6.4 Study Intervention Compliance

Only participants enrolled in the study may receive study treatment and only ophthalmologists who have experience administering intravitreal injections may administer study treatment.

The unmasked Investigator is responsible for administering the correct dose of KSI-301 or sham administration, according to the study protocol. The date and time of each dose administered in the clinic will be recorded in the source documents and electronic case report form (eCRF). To avoid medication dispensing errors, the study intervention, study participant and Study Eye identification will be confirmed at the time of dosing by a member of the unmasked study site team.

6.5 **Dose Modification**

Participants can only receive the specified dose for the intervention group, as follows:

- A. KSI-301: 5 mg
- B. Sham injection

Alterations of the dosage are not allowed.

6.6 Continued Access to Study Intervention after the End of the Study

After participants complete their final follow-up visit or discontinue from the study prematurely, they will return to standard of care treatment at the discretion of their treating physician. The Sponsor will not provide continued access to study treatment following the end of the study or the end of each participant's study treatment period.

6.7 Treatment of Overdose

For this study, any dose of KSI-301 greater than 5 mg at a single study visit will be considered an overdose.

The Sponsor does not recommend any specific treatment for an overdose.

In the event of an accidental overdose, the Investigator/treating physician should:

- Contact the Medical Monitor immediately.
- Evaluate the participant to determine, in consultation with the Medical Monitor, whether additional steps should be taken.
- Closely monitor the participant for any AE/SAE.
- Document the quantity of the excess dose.

In addition to overdosing, an increased injection volume may cause an increase in intraocular pressure. In case of overdose, intraocular pressure should be monitored and if deemed necessary by the treating physician, adequate treatment should be initiated, including performing pressure lowering procedures (i.e., anterior chamber paracentesis).

6.8 Concomitant Therapy

Use of all concomitant medications will be recorded in the participant's eCRF, except for medications required for carrying out procedures in the SoA (Section 1.3) (e.g., dilating drops, anesthetics, antiseptic, fluorescein, etc.) related to this study. Concomitant medications will include all prescription drugs, herbal products, vitamins, minerals, and over the counter (OTC) medications as used by the participant within 30 days prior to Day 1 through Week 100. Any changes in concomitant medications also will be recorded in the participant's eCRF.

Any concomitant medication deemed necessary for the welfare of the participant during the study may be given at the discretion of the Investigator. However, it is the responsibility of the Investigator to ensure that all relevant details regarding the medication are recorded in the eCRF. Participants who use oral contraceptives, hormone-replacement therapy, or other maintenance therapy should continue their use.

In case the fellow eye (non-Study Eye) requires anti-VEGF treatment during the conduct of the study, the participant may be treated at the discretion of the Investigator and according to the standard of care in the respective country. The treatment of the fellow eye (non-Study Eye) may be implemented at any time once the Day 1 injection has been administered. Anti-VEGF treatment for the fellow eye, including the date of each administration, must be documented as a concomitant medication on the appropriate eCRF. If the fellow eye requires treatment during the same visit as the Study Eye, the Study Eye should be treated first, and the fellow eye should be treated by the unmasked physician to preserve masking.

The Medical Monitor should be contacted if there are any questions regarding concomitant or prior therapy.

6.8.1 Pan-retinal Photocoagulation

Pan-retinal photocoagulation (PRP) laser is permitted in the Study Eye if PDR or ASNV develops. PRP will be reported as a concomitant procedure in the appropriate eCRF.

6.8.2 **Prohibited Therapy**

At the discretion of the Investigator, during the Study participants may start or continue to receive all medications and standard treatments administered for other conditions, except for the following:

- Investigational therapies in the non-Study Eye;
- Intravitreal anti-VEGF drugs other than study-assigned KSI-301 in the Study Eye;
- Systemic anti-VEGF therapy;
- Intravitreal or periocular steroids or steroid implants in the Study Eye;

- Concurrent use of macular laser photocoagulation in the Study Eye; and
- Investigational treatment with any drug (other than vitamins and minerals) or device.

Participants whose medical care requires use of a prohibited therapy must have study treatment interrupted or be discontinued from the study in order to receive that therapy. After discussion with the Sponsor, participants whose study treatment has been interrupted but no longer need a prohibited therapy may resume study treatment.

6.8.3 Supportive Care for Adverse Events

Supportive care for the known potential risks associated with anti-VEGF treatment and KSI-301 (summarized in Table 2) should be as per the standard of care in the respective country. No specific prophylactic therapies are recommended.

7.0 DISCONTINUATION OF STUDY INTERVENTION AND PARTICIPANT DISCONTINUATION/WITHDRAWAL

7.1 Discontinuation of Study Intervention

Participants may withdraw from the study at any time and for any reason without prejudice to their future medical care by the Investigator or at the study site. Every effort should be made to keep participants in the study.

If study treatment is discontinued, an end-of-treatment visit should occur 28 +/- 7 days after study treatment is discontinued or before a new treatment regimen begins. Participants who discontinue study drug should NOT be considered withdrawn from the study. Unless they withdraw consent or there is additional risk to the participant, participants who have discontinued study treatment should be encouraged to stay in the study and undergo as many scheduled visits as possible, with emphasis on the Week 48 (primary endpoint) and Week 96 (secondary endpoint) visits.

The reasons for study treatment discontinuation and/or withdrawal from the study (study discontinuation) will be recorded on the appropriate eCRF.

A participant may be withdrawn from the study for any of the following reasons:

- 1. The participant is non-compliant with the protocol;
- 2. The participant has a serious or intolerable adverse event(s) (AE[s]) that in the Investigator's opinion requires withdrawal from the study;
- 3. The participant has symptoms or an intercurrent illness not consistent with the protocol requirements or that justify withdrawal;
- 4. The participant is lost to follow-up;
- 5. Any medical condition that the Investigator or Sponsor determines may jeopardize the participants' safety if they remain in the study;
- 6. The participant withdraws consent, or the Investigator or Sponsor decides to discontinue the participant's participation in the study; or
- 7. Pregnancy.

The Investigator will also withdraw a participant if the Sponsor terminates the study. Upon occurrence of a serious or intolerable AE, the Investigator will confer with the Sponsor. If a participant is discontinued because of an AE, the event will be followed until it is resolved, or no additional improvement is expected by the Investigator (based on a follow-up period of not less than 3 months). Any participant may withdraw his or her consent at any time.

7.1.1 Treatment Interruption and/or Discontinuation due to Adverse Events or Concomitant Procedures

Study treatment interruption and/or participant discontinuation from the study treatment due to certain adverse events or concomitant procedures in the Study Eye will be determined using the criteria provided in Table 5. If any of these are met, treatment will be interrupted (or discontinued if applicable) and notification will be sent to the medical monitor. Treatment may be resumed after resolution of the adverse event and upon agreement with both the Investigator and medical monitor. The reason for study treatment interruption or discontinuation should be recorded on the appropriate eCRF and, if applicable, on the Adverse Event eCRF.

Event (MedDRA Preferred Term)	Study Treatment Interruption Criteria	
Vision loss	Interrupt study treatment for treatment-related decrease of \geq 30 letters in BCVA in the Study Eye compared with the most recent prior visit.	
Intraocular inflammation	Interrupt study treatment if any active intraocular inflammation is present in the Study Eye.	
Intraocular surgery	Interrupt study treatment for intraocular surgery in the Study Eye, for example cataract surgery.	
	Treatment may resume no earlier than 10 days after uncomplicated cataract surgery, provided there is no evidence of post-operative intraocular inflammation. For complicated cataract surgery or following other intraocular surgery, study treatment may be resumed as determined by the	
	Investigator following discussion with the Medical Monitor.	
Elevated intraocular pressure	Interrupt study treatment if the pre-injection IOP is >30 mmHg in the Study Eye.	
Retinal tear or break	Interrupt study treatment if a retinal tear or break is present in the Study Eye.	
	Treatment may be resumed no earlier than 10 days after successful laser retinopexy, as determined by the Investigator.	
Retinal detachment or macular hole	Interrupt study treatment if rhegmatogenous retinal detachment or Stage 3 or Stage 4 macular hole occurs in the Study Eye.	
	Treatment may be resumed no earlier than 14 days after successful treatment, as determined by the Investigator, following discussion with the Medical Monitor.	
Active infection	Interrupt study treatment if infectious cellulitis, conjunctivitis, keratitis, scleritis, or endophthalmitis occurs in or around either eye. Infections should be treated as per the local standard of care.	

Table 5: Protocol KS301P106: Treatment Interruption Criteria

7.2 Participant Discontinuation/Withdrawal from the Study

Participants should be strongly encouraged to stay in the study and undergo as many scheduled visits as possible, with emphasis on the Weeks 48, 96, and 100 safety assessments. However, participants are free to withdraw from the study or study treatment at any time upon request. Participant participation in the study may be stopped at any time at the discretion of the Investigator or at the request of the Sponsor.

Participants who discontinue study treatment or active participation in the study will no longer receive study intervention. When a participant discontinues from study treatment or active participation in the study, the reason(s) for study treatment discontinuation or withdrawal shall be recorded by the Investigator or designee on the relevant page of the eCRF. Whenever possible, all participants who discontinue study treatment or withdraw from the study prematurely will undergo an ET visit. Participants who fail to return for final assessments must be contacted by the site by phone and in writing to obtain follow-up.

If a participant exits early from the study between visits, the Investigator or designee must attempt to contact the participant and advise the participant to return for a final visit to complete the exit procedures. If the participant is unable or unwilling to return for the Early Termination visit, the 'date of exit' will be the date that the participant was last seen at the site or contacted by other communication.

If the participant withdraws consent for disclosure of future information, the sponsor may retain and continue to use any data collected before such a withdrawal of consent.

If a participant withdraws from the study, he/she may request destruction of any samples taken and not tested, and the Investigator must document this in the site study records.

7.3 Lost to Follow up

A participant will be considered lost to follow-up if he or she repeatedly fails to return for scheduled visits and is unable to be contacted by the study site.

The following actions must be taken if a participant fails to return to the clinic for a required study visit:

a) The site must attempt to contact the participant and reschedule the missed visit as soon as possible and counsel the participant on the importance of maintaining the assigned visit schedule and ascertain whether the participant wishes to and/or should continue in the study.

- b) Before a participant is deemed lost to follow up, the Investigator or designee must make every effort to regain contact with the participant (where possible, three telephone calls and, if necessary, a certified letter to the participant's last known mailing address or local equivalent methods) and discuss the situation with the Sponsor. These contact attempts should be documented in the participant's medical record.
- c) Should the participant continue to be unreachable, he/she will be considered to have withdrawn from the study.

Discontinuation of specific sites or of the study are handled as part of Appendix 1.

8.0 STUDY ASSESSMENTS AND PROCEDURES

- Before undertaking any study procedures, all potential participants will sign an ICF. Participants will have the opportunity to have any questions answered before signing the ICF. The Investigator or designee must address all questions raised by the participant. The Investigator or designee will also sign the ICF.
- Study procedures and their timing are summarized in the SoA (Section 1.3). Assessments performed in the event of an unscheduled safety visit (Appendix 5) are at the discretion of the Investigator. Adherence to the study design requirements, including those specified in the SoA, is essential and required for study conduct. All screening evaluations must be completed and reviewed to confirm that potential participants meet all eligibility criteria. The Investigator will maintain a screening log to record details of all participants screened and to confirm eligibility or record reasons for screening failure, as applicable.
- Protocol waivers or exemptions are not allowed.
- Immediate safety concerns should be discussed with the Sponsor immediately upon occurrence or awareness to determine if the participant should continue or discontinue study intervention.

8.1 Efficacy Assessments

Planned time points for all efficacy assessments are provided in the SoA (Section 1.3).

8.1.1 Medical History and Demographic Data

Medical history (general and ophthalmic) includes clinically significant diseases, surgeries, and reproductive status. All medications (e.g., prescription drugs, OTC drugs, herbal or homeopathic remedies, nutritional supplements) used by the participant regularly or within 30 days preceding Day 1 will be recorded. A full ocular history including prior ocular treatments will be noted. Demographic data will include age, sex, and ethnic origin (also referred to as self-reported race and ethnicity in some regions of the world).

8.1.2 **Ophthalmic Exams**

Unless otherwise noted, ophthalmic assessments are captured for the Study Eye only.

Slit-lamp examination will include the following:

- Inspection of the eyelids,
- Inspection of the cornea,
- Examination of the anterior chamber,
- Examination of the pupil,
- Examination of the iris,
- Inspection of the lens,

- Inspection of the vitreous body,
- Inspection of the retina, and
- Inspection of the optic disc.

Dilated indirect ophthalmoscopy will include examination of the peripheral retina and vessels.

Tonometry shall be conducted as part of the ophthalmic exam. The method of IOP measurement (such as Goldmann tonometry or Tonopen) must remain the same throughout the study for each participant. Pre-injection tonometry should be performed prior to pupil dilation.

Participants will be instructed to report any signs or symptoms of intraocular inflammation (uveitis) or endophthalmitis such as pain, photophobia, redness, or reduced vision.

8.1.3 Injection Procedure

The unmasked injecting Investigator must be qualified and trained in administering intravitreal injections and follow standard injection procedures in adherence to specific institutional or local policies associated with intravitreal injections. Aseptic technique must be observed by clinic staff involved in the assembly of the injection tray, study intervention preparation, anesthetic preparation, and study treatment administration. To minimize the risk of infection the periocular skin, eyelid and conjunctiva of the Study Eye must be disinfected, as outlined in the Pharmacy Manual.

The unmasked injecting Investigator will choose one of the acceptable methods of ocular anesthesia on a per participant basis. Subconjunctival anesthesia is recommended (but not required) to maximize participant comfort. In order to maintain masking, the selected method of anesthesia for an individual participant must remain constant for the duration of the trial and at all visits irrespective of the study treatment assigned during the study visit (KSI-301 or sham) and documented in the site's source documents. Per Section 4.1.3.1, upon initiation of treatment of DME, PDR, and/or ASNV, the method of anesthesia is not required to remain constant.

Please refer to the Pharmacy Manual for Investigational Medicinal Product (IMP) preparation and administration.

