4.1.3 Administration of Study Intervention

All participants will be treated starting on Day 1 through Week 92 according to their respective treatment group. The IRT will determine the dosing schedule and adjust it in consideration of missed visits, out of window visits, and missing data during a visit. If a visit is missed at which study treatment is scheduled to be administered, the missed dose should be made up as close to the originally scheduled visit as possible using an unscheduled visit. Adjustments to study intervention due to development of sight-threatening complications of DR are described in Section 4.1.3.1.

As shown in the dosing regimen schematic provided in Figure 1, participants will be treated according to the group to which they were randomized, as follows:

• Group A - KSI-301 5 mg via Intravitreal Injection:

Intravitreal KSI-301 5 mg injection will be administered on Day 1, Week 8, Week 20, Week 44, Week 68, and Week 92.

• Group B - Sham Injection:

To preserve study masking, sham injections are administered to Group B participants at visits in which KSI-301 is administered to Group A participants. Thus, sham injections will be administered on Day 1, Week 8, Week 20, Week 44, Week 68, and Week 92.

For all study participants, non-treatment study visits will occur on Week 32, Week 48, Week 56, Week 80, and Week 96. A final safety assessment will occur on Week 100 and will be done via telephone call for all participants, except in WOCBP, in which case a site visit is required to administer a pregnancy test.

		Year 1								PE				
Week		0	(4)	8	(12)	(16)	20	(24)	(28)	32	(36)	(40)	44	48
KSI-301 5 mg	Q24W													
Sham		0		0			0						0	
						Ĩ	Year 2						SE	SA
Week		(52)	56	(60)	(64)	68	(72)	(76)	80	(84)	(88)	92	96	100 ª
KSI-301 5 mg	Q24W													
Sham						0						0		

Figure 1: Protocol KS301P106: Masked Dosing Regimens by Week

Abbreviations: PE = primary endpoint; Q24W = once every 24 weeks; SA = safety assessment; SE = secondary endpoint.

^a Week 100 is a final safety assessment that will be done via telephone call for all participants, except in WOCBP, in which case a site visit is required for the safety assessment that includes a pregnancy test.

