6.1 Study Intervention(s) Administered

Study interventions are summarized in Table 4. For full information regarding the administration of study intervention and the contents of the kit, refer to the Pharmacy Manual. The full instructions for administration of sham are also described in the Pharmacy Manual.

Table 4:Protocol KS301P106: Study Interventions

Group Name	А	В
Intervention Name	KSI-301 5 mg	Sham
Туре	Biological medicinal product	Sham
Dose Formulation	Sterile liquid for intravitreal injection in single-use vials	Empty vial
Unit Dose Strength(s)	mg/mL (based on antibody mass)	N/A
Dosage Level(s)	5 mg	N/A
Route of Administration	Intravitreal injection	Sham injection
Use	Experimental	Sham (to maintain study masking)
IMP and NIMP	IMP	NIMP
Sourcing	Provided centrally by the Sponsor	Provided centrally by the Sponsor
Storage	In the original packaging, as provided, until the time of use. Store at 2-8°C before use. Refer to Pharmacy Manual for additional instructions.	In the original packaging, as provided, until the time of use. Store at 2-8°C before use. Refer to Pharmacy Manual for additional instructions.
Packaging and Labeling	KSI-301 will be provided in vials that will be labeled as required per country requirement.	Sham will be provided in vials that will be labeled as required per country requirement.
Reconstitution and Handling	KSI-301 is an aqueous solution that is provided in vial and filled into a syringe by unmasked site personnel without reconstitution or dilution.	Sham is provided as empty glass vials, which will remain empty throughout the sham treatment procedure. A sham injection mimics an intravitreal injection. It involves pressing the blunt end of an empty syringe, without a needle, against an anesthetized eye.
Current/Former Name(s) or Alias(es)	N/A	N/A

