6.3.2 Masking and Unmasking

This is a double-masked study. There must be a minimum of two Investigators per site to fulfill the masking requirements of this study, as follows:

- **Masked Evaluating Physician(s)**: At least one Investigator will be designated as the evaluating physician who will be *masked* to participants' treatment assignments and will evaluate all ocular assessments (other than the immediate post-injection assessment done by unmasked personnel, as described below).
- Unmasked Treating Physician(s): At least one other Investigator will be designated as the treating (injecting) physician who will be *unmasked* to participants' treatment assignments and will administer study intervention (KSI-301 or sham). This physician or an unmasked assistant will also conduct the immediate post-injection assessments, including tonometry, in the Study Eye (Section 8.1.4). The unmasked treating physician and unmasked staff must not divulge treatment assignment to anyone.

As shown in Section 6.1, there are two study interventions: (1) KSI-301 (the investigational medicinal product); and (2) sham (for which an injection procedure is simulated but not actually performed). The two study interventions are provided are provided in unmasked vials within masked cartons (also referred to as kits), as follows:

• **Masked Cartons**: All study interventions are provided in cartons that are identical in appearance and weight, making them indistinguishable from each other.

Each carton is labeled with an identical carton label that includes a unique kit number. The IRT system will direct site personnel which specific carton to pull from inventory and use for

a specific participant at a given visit based on the unique kit number printed on the carton label and that participant's treatment at that given visit.

• Unmasked Vials Within the Masked Cartons: Owing to differences among vials, syringes, dose-preparation procedures, and treatment procedures that cannot be masked, the treating (injecting) physician is unmasked to study treatment as are any assistants to the treating (injecting) physician. Only unmasked site staff are allowed to open the masked cartons.

Participants, study site personnel (except for the treating physician(s), assistant(s), and pharmacist if any), the designated evaluating physician(s), central reading center personnel, and the Sponsor and its agents will be masked to treatment assignment.

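### The unmasked injector chooses each participant's anesthesia, and the constancy rule meant to protect masking does not keep it comparable between arms

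*Protocol*

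**What the plan says.** Protocol section 8.1.3 assigns the choice: "The unmasked injecting Investigator will choose one of the acceptable methods of ocular anesthesia on a per participant basis". Section 6.3.2 confirms what that person knows: "the treating (injecting) physician is unmasked to study treatment as are any assistants to the treating (injecting) physician". The choice is open, because section 8.1.3 adds: "Subconjunctival anesthesia is recommended (but not required) to maximize participant comfort".

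The safeguard, introduced in section 8.1.3 as a masking measure, is that "the selected method of anesthesia for an individual participant must remain constant for the duration of the trial and at all visits", whether KSI-301 or sham is given at the visit. The method is to be documented in the site's source documents.

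On the procedures themselves, section 4.1.3 says that "sham injections are administered to Group B participants at visits in which KSI-301 is administered to Group A participants". Table 4 in section 6.1 describes the sham: "It involves pressing the blunt end of an empty syringe, without a needle, against an anesthetized eye".

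Section 6.8 has concomitant medications recorded in the eCRF "except for medications required for carrying out procedures in the SoA (Section 1.3) (e.g., dilating drops, anesthetics, antiseptic, fluorescein, etc.) related to this study". SAP section 8.2 tabulates study-eye events and injection-procedure-related study-eye events by arm. It plans no summary by anesthesia method.

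**The concern.** The protocol itself treats anesthesia as a possible threat to masking, since it has a rule for that purpose. The rule works along the wrong axis for this design. Keeping the method constant within a person protects masking when the same person receives active drug at some visits and sham at others. Here nobody in the masked period is scheduled to do so. What needs protecting is comparability between the arms, and the rule does not address that. If an injector picked a different method for a needleless sham than for a real injection, the rule would carry that difference from Day 1 to the last masked visit.

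Two things would be at stake. First, local ocular events caused by the anesthetic would appear as a difference between KSI-301 and sham in the study-eye and procedure-related tables. Second, the method could act as a cue to the arm for the participant, or for staff who see the participant at an early unscheduled visit. As far as the documents show, the planned dataset could not reveal either problem, because the method is required only in source documents.

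**Working it through.** The plan gives no figure on this point, so there is nothing to reproduce. The check has four steps.

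**1. Does the safeguard reach between arms?** Inputs from protocol section 4.1.3:
- Group A is scheduled for KSI-301 on Day 1 and at Weeks 8, 20, 44, 68 and 92.
- Group B is scheduled for sham at the same six visits.

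Each masked participant therefore has one procedure type throughout. Constancy within a participant holds equally well whether the two arms have the same mix of methods or entirely different ones. It places no limit on the difference between arms.

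**2. Size of an adverse event shift.** Let s be the share of an arm given subconjunctival anesthesia, r_sub the risk of a local event with it, and r_other the risk with the other method.

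- Arm rate = s × r_sub + (1 − s) × r_other
- Difference between arms = (s_A − s_B) × (r_sub − r_other)

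The documents give none of these values, so all are assumptions. For a 30-point gap and r_other = 5%:
- r_sub = 10%: 0.30 × (0.10 − 0.05) = 0.015, or 1.5 points (120 × 0.015 = 1.8 participants per arm of about 120)
- r_sub = 30%: 0.30 × (0.30 − 0.05) = 0.075, or 7.5 points (120 × 0.075 = 9 participants)

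One fuller example has shares of 80% and 40%, and risks of 20% and 5%:
- KSI-301 arm: 0.80 × 0.20 + 0.20 × 0.05 = 17.0%
- Sham arm: 0.40 × 0.20 + 0.60 × 0.05 = 11.0%
- Difference with no drug effect: 6.0 points, about 7 participants per 120. The chance of p < 0.05 is 27% at 120 per arm.

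With equal shares, or with equal risks for the two methods, the difference is 0.

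**3. Size of the cue.** Under 1:1 allocation, an observer who knows the mix in both arms and guesses from the method alone is right with probability 0.5 + (s_A − s_B)/2. For the assumed 30-point gap this is 0.5 + 0.15 = 65%. It is an upper bound for participants, who see only their own method and are not told the mix in the other arm.

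**4. Could the masked Investigator see it at scheduled visits?** The gaps from each masked treatment to the next scheduled masked examination (protocol section 1.3.1) are:
- Day 1 to Week 8: 8 weeks
- Week 8 to Week 20, Week 20 to Week 32, and Week 68 to Week 80: 12 weeks each
- Week 44 to Week 48, and Week 92 to Week 96: 4 weeks each

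Unmasked staff do the immediate post-injection checks (section 6.3.2). The documents do not say that anesthesia leaves signs lasting 4 to 12 weeks.

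**The case against.** The strongest reply is that nothing shows injectors would choose differently by arm. One recommendation covers all participants without regard to arm, and the sham eye is anesthetized too. The Pharmacy and Masking Manuals are not supplied and may restrict the methods or fix when the choice is made. Section 8.1.3 does not say that the choice follows knowledge of the arm: cartons look identical, and the contents show only once unmasked staff open them. A needle against a blunt syringe already makes procedure-related events differ by arm. All of this stands and lowers the likelihood of a problem. None of it gives the constancy rule a function between arms.

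A reader might infer more than the documents support:

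- **Biased diagnoses of DME, PDR or ASNV.** The masked Investigator makes these diagnoses, and they feed two key secondary endpoints. But the scheduled examinations fall 4 to 12 weeks after treatment, the diagnoses need imaging or clinical documentation, and DME has numeric thickness thresholds. Unmasking of the evaluator at these visits is not shown.
- **A biased primary endpoint.** A masked reading center grades the photographs. A site diagnosis does trigger carry-forward of DRSS, but that route needs the diagnosis to be biased first.
- **Anesthetic events charged to KSI-301.** Appendix 3 has relationship assessed to the injection procedure as well as to the study intervention, so misattribution could happen but does not follow.
- **A larger event difference.** Multiplying the gap by the subconjunctival risk alone (0.30 × 0.10 to 0.30 × 0.30) gives 3 to 9 points. That treats the other method as free of events, which nothing in the documents supports.

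**Conclusion.** The point holds as a gap in the masking procedure. A physician who is unmasked to treatment may choose the method, and the only stated safeguard does not do what this parallel design needs. Whether anesthesia differs by arm is unknown; the documents allow it but do not show it.

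If it did differ, the exposure lies mainly in local study-eye and procedure-related adverse event comparisons: 1.5 to 7.5 points under the assumed 30-point gap and assumed risks of 10% to 30% against 5%. Across wider assumptions (shares from 70/50 to 100/0, risks from 10%/2% to 30%/5%) the range is 1.6 to 25.0 points. These figures are illustrations, not predictions. A cue to participants, or to staff at early unscheduled visits, is a second possible effect. The conclusion also depends on the two manuals not already fixing or timing the choice.

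**What to change.** In protocol section 8.1.3, require the anesthesia method to be chosen and recorded before the IRT randomization call, and at the latest before the carton is opened. Keep it through the masked period and record the reason for any change. Capture it in a dosing eCRF field that only unmasked staff can access. In the SAP, tabulate method by arm beside the study-eye and procedure-related treatment-emergent events. No particular anesthetic needs to be named.

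SAP section 3.1 reports that development of KSI-301 has been discontinued, so the prospective change may come too late. If enrolment is complete, retrieve the method from source documents and report it by arm with the study-eye events.

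The cost is wording in the protocol and the Masking Manual, one eCRF field and one table. The downside is slightly less freedom for the injector to adapt the method once the arm is known.
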